1.2. Rationale and justification for the Study

a. Rationale for the Study Purpose

So far, there is no strong evidence supporting the clinical impact of any dressings or membranes on the healing of the FGG donor site. It is very important to assess the effects of the allogenic amnion chorion membrane on the wound of the FGG donor site given this membrane has the potential to improve wound healing and reduce complications.

b. Rationale for Materials Selected

The ACM (allogenic amnion chorion membrane, BioXclude®, SNOASIS MEDICAL) is a commercial product and has multiple sizes available. It has been used for tissue healing and tissue regeneration in dentistry. Based on the available evidence, it has the potential to improve wound healing of the FGG donor site. The collagen dressing, CLD (Collagen Patch®, Zimmer), is a common product used for tissue healing in dentistry (Shanmugam et al. 2010). It is selected as a dressing material to cover the wound in the control group.

c. Rationale for Study Population

The study will recruit subjects who need free gingival graft surgery. The dressings, ACM or CLD, will be placed in the wound of the FGG donor site. These subjects

should be systemically healthy and are able to receive FGG surgery.

d. Rationale for Study Design

It is a randomized controlled and split-mouth design study. The randomized controlled trial (RCT) is usually considered the gold standard for a clinical trial and it is able to provide the highest level of evidence within all the study designs (Howick et al. 2011). The split-mouth design is a popular design in oral health research. Two treatments (test and control) are randomly assigned to either the right or left halves of the dentition/palate. This design removes a lot of inter-individual variability from the estimates of the treatment effect given two treatments are performed in the same subject (Lesaffre et al. 2009).

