11. SAMPLE SIZE AND STATISTICAL METHODS

11.1. Determination of Sample Size

The pilot project will use a convenient sample size based on the budget. We will recruit 19 patients in total, and with a dropout rate of 15%, we will have a sample size of 15.

With 15 patients, we can detect an effect size as small as 0.7 between two treatments for the two main outcomes (the area of healing and VAS pain score at

week 2), by a paired t test assuming a within-subject correlation of 0.6 at the significance level of 0.05 with 80% power. Considering this is a pilot study, Bonferroni correction is not necessary.

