11.2. Statistical and Analytical Plans

a. General Considerations

We will present means and standard deviations for completeness of the report. The statistical significance level to test the primary endpoint was set at $p<0.05$, a priori.

b. Safety Analyses

Safety will be evaluated by tabulations of adverse events and will be presented with descriptive statistics at baseline and follow-up visits each month.

Adverse events will be classified as severe complications and summarized for baseline and follow-up visits.

All information pertaining to adverse events noted during the study will be listed by subject, detailing verbatim given by the investigator, preferred term, date of onset, date of resolution, severity, and relationship to procedure. The onset of adverse events will also be shown relative (in number of days) to the day of performing the surgery.

A tabulation of Serious Adverse Events (SAEs) will be provided by subject within treatment groups. The proportion of subjects in each treatment group reporting adverse events that occur in ~ 3% in either treatment group will be compared using Bayesian methods. The specific preferred terms analysed will be those that are reported by at least five percent of the subjects in either treatment group.

c. Statistical Analysis Plan:

We will explore the difference between the two treatments for outcomes including the degree of epithelialization, the size of wound area, color match, bleeding condition, pain, sensibility, and outcomes from Gingival specimens by paired t test or McNemar's test depending on the variables.

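### The two adverse event cut-offs in section 11.2 b are unreconciled and do not filter at 15 to 19 patients, and the Bayesian comparison they lead to is unspecified and does not mention the within-patient pairing

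*Combined protocol and SAP*

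**What the plan says.** Section 11.2 b (Safety Analyses) plans a listing of all adverse events by subject, descriptive tabulations, and then a comparison between treatment groups. Two adjacent sentences govern that comparison. The first says that proportions of subjects with "adverse events that occur in ~ 3% in either treatment group will be compared using Bayesian methods". The second says: "The specific preferred terms analysed will be those that are reported by at least five percent of the subjects in either treatment group". Nothing links the two, and no section gives a prior, a likelihood, a posterior summary or a decision rule.

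On numbers, section 11.1 says: "We will recruit 19 patients in total, and with a dropout rate of 15%, we will have a sample size of 15". On design, section 1.2 d says: "Two treatments (test and control) are randomly assigned to either the right or left halves of the dentition/palate". Each patient therefore contributes one membrane side and one collagen side. Section 3.6 allows withdrawn subjects to be replaced, so the number treated could exceed 19.

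**The concern.** A percentage cut-off for adverse event terms is meant to keep isolated events out of a between-group comparison. Here there are two, with different values and no statement of how they combine, and the groups are so small that one patient is a larger percentage than either.

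A term with one affected subject therefore meets the 5% rule and goes to a comparison described only as Bayesian. With so little data, the answer would depend heavily on a prior that could be chosen after the events are known. The clause speaks of proportions in each treatment group, as if these were separate sets of patients, although the data are pairs of sides within a palate. An event that belongs to neither side, such as one at the recipient site, has no group at all.

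The stake is the part of the alternative hypothesis in section 2.1 that expects fewer complications with the membrane. A posterior probability from one or two events could be read as support for it.

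**Working it through.** **Inputs.** 19 recruited, 15% dropout and 15 analysed (section 11.1); cut-offs of about 3% and at least 5% (section 11.2 b); both dressings in every patient (section 1.2 d). The plan gives no expected event rates and no prior, so the event counts and priors below are assumptions.

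**The plan's own figure.** Section 11.1 says "With 15 patients, we can detect an effect size as small as 0.7 between two treatments", "assuming a within-subject correlation of 0.6 at the significance level of 0.05 with 80% power". With a paired t test, the standardised within-patient difference is 0.7 / √(2 × (1 − 0.6)) = 0.783. At n = 15 (14 degrees of freedom) the two-sided power is 80.5%, so the figure reproduces. Dropout gives 19 × 0.85 = 16.15 against 15 stated, which is close. This calculation covers wound area and pain; there is none for adverse events.

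**Step 1: smallest non-zero proportion, 1/n.**
- n = 15: 6.67%
- n = 16: 6.25%
- n = 17: 5.88%
- n = 18: 5.56%
- n = 19: 5.26%

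An observed proportion is therefore either 0% or at least 5.26%.

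**Step 2: apply the cut-offs.**
- At least 5%: 5% of 19 is 0.95 patients, so one affected subject is enough. No observed term is removed.
- About 3%, read literally: 3% of 19 is 0.57 patients. No attainable proportion is near 3%, so nothing is selected.
- At least 3%, if the tilde stands for that sign: one affected subject is enough, so everything observed is selected.
- With replacement: at n = 21 one subject is 1/21 = 4.76%. The 5% rule then needs two subjects and an at-least-3% rule still needs one, so the rules diverge.

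**Step 3: how easily the 5% rule is met.** Suppose a term has a true rate of 1% per side and sides are independent (both assumed). The chance of at least one affected side is 1 − 0.99^30 = 26% at n = 15 and 1 − 0.99^38 = 32% at n = 19.

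**Step 4: one patient affected on one side only.** Let θ be the share of discordant patients whose event is on that side, with an assumed Beta(a, a) prior. The posterior is Beta(a + 1, a), and P(θ > 0.5) is:
- Beta(2,2): 0.688
- Beta(1,1): 0.750
- Beta(0.5,0.5): 0.818

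More extreme priors run from 0.59 with Beta(10,10) to 0.99 with Beta(0.01,0.01). The two-sided exact McNemar p-value for one discordant patient is 2 × 0.5 = 1.0.

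**Step 5: no events on a side.** The two-sided exact 95% upper limit is 1 − 0.025^(1/n): 21.8% for 0/15 and 17.6% for 0/19.

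**The case against.** The strongest case for the plan has five parts.

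- **The sentences may be nested.** The first may name the comparison and the second narrow it to particular terms. The plan does not say so. If the tilde means at least, nesting changes nothing at 15 to 19 patients, because both rules select the same terms. A reader might infer that the two cut-offs give contradictory selections in this trial. On that reading they do not; they diverge only from 21 treated patients.
- **The tilde may be a misread or mistyped sign.** That is possible but not proven, since the at-least sign survives in section 3.3. The cut-off fails on either reading, but in different ways: it selects nothing or it selects everything observed.
- **No event is hidden.** This stands. Section 11.2 b lists every event by subject with onset, resolution, severity and relationship to the procedure.
- **The complications hypothesis does not rest on this clause.** This largely stands. Section 11.2 c compares bleeding, pain and sensibility by paired t or McNemar's test, in exploratory terms. Some overlap remains: continuous bleeding is also a severe complication in section 9.2, so a bleeding event could enter both analyses, and the plan does not say which governs.
- **One against none is a chosen case.** This stands. Events may be more frequent, since section 9.2 counts pain above 6 on the VAS as a severe complication. Posterior probabilities of 69% to 82% would not normally carry a claim.

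**Conclusion.** The point holds with modest weight. Neither cut-off works as a filter at the planned size: the 5% rule removes no observed term, and the 3% rule selects nothing or everything observed, depending on how the tilde is read. The 5% rule thus sends any term with one affected subject to a Bayesian comparison that is unspecified and does not mention the pairing. Under assumed priors, one discordant patient gives 69% with Beta(2,2) to 82% with Beta(0.5,0.5), against p = 1.0 from exact McNemar.

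The cut-off arithmetic is exact for 15 to 19 treated patients. The posterior figures rest on assumed priors and an assumed event pattern.

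A reader might infer that the trial will make a false safety claim, or that its complications hypothesis will be decided by the prior. The documents do not support that: they set no decision threshold, they call the trial a pilot, they list all events, and they compare the main complications separately in section 11.2 c. Nor is a stated figure miscalculated. The fault is that the thresholds do not fit the sample size and the comparison is not specified.

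**What to change.** Change section 11.2 b as follows.

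1. Delete both cut-offs.
2. Tabulate every donor-site event term as within-patient counts: membrane side only, collagen side only, both sides, neither side. Give the exact 95% interval for each side's proportion, including when no events are seen.
3. List events that cannot be assigned to a palatal side, such as recipient-site or systemic events, separately by subject.
4. State that the adverse event comparison is descriptive and supports no between-dressing safety claim at this sample size.

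If the sponsor prefers to keep a Bayesian comparison, it should use a paired model, with the prior and the posterior summary fixed before the data are seen.

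The cost is SAP wording. The table is simpler to produce than the comparison it replaces and needs no extra patients, provided that the palatal side of each donor-site event is recorded. The downside is that the stated safety comparison becomes descriptive.

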12. ETHICAL CONSIDERATIONS

12.1. Informed Consent

Informed consent is a process that is initiated prior to the individual's agreeing to participate in the study and continues throughout the individual's study participation. Extensive discussion of risks and possible benefits of study participation will be provided to the subjects and their families. A consent form describing in detail the study interventions, procedures, and risks will be given to the subject. Consent forms will be IRB-approved, and the subject will be asked to read and review the document. The investigator or designee will explain the research study to the subject and answer any questions that may arise. The subject will sign the informed consent document prior to any study-related assessments or procedures. Subjects will be given the opportunity to discuss the study with their surrogates or think about it prior

to agreeing to participate. They may withdraw consent at any time throughout the course of the trial. A copy of the signed informed consent document will be given to subjects for their records. The rights and welfare of the subjects will be protected by emphasizing to them that the quality of their clinical care will not be adversely affected if they decline to participate in this study.

The consent process will be documented in the clinical or research record.

This documentation will include the following:

A notation of the date that the consent was obtained

A statement that the consent was obtained prior to the initiation of study procedures

A statement that the subject had adequate time to review the consent and that all questions were answered prior to initiation of study procedures

A notation confirming that a copy of the signed consent was given to the subject

12.2. IRB review

The protocol, informed consent form(s), and all advertising and subject materials will be submitted to the IRB for review and approval. Approval of both the protocol and informed consent form must be obtained before the enrollment of any subject. Any amendment to the protocol will require review and approval by the IRB before the changes are implemented in the clinic.

12.3. Confidentiality of Data and Patient Records

The subject's name will appear only on the consent form and clinical record, both of which will be kept separate from collected study data. All subject files will be kept confidential and placed in a double-locked office. A unique coded study number will be assigned to each subject for data collection. The number will not contain any personal information (e.g., dates, age) to further ensure protection.

The study protocol, documentation, data, and all other information generated will be held in strict confidence. No information concerning the study or the data will be released to any unauthorized third party without prior written approval of the PI. No subject names will be used in publications or presentations.

13. PUBLICATIONS

Following completion of the study, the investigator is expected to publish the results of this research in a scientific journal. The International Committee of Medical Journal Editors (ICMJE) member journals have adopted a trials-registration policy as a condition for publication. This policy requires that all clinical trials be registered in a public trials registry such as ClinicalTrials.gov (De Angelis et al. 2004), which is sponsored by the National Library of Medicine. Other biomedical journals are considering adopting similar policies. For grants and cooperative agreements, it is the institution's responsibility to register the trial in an acceptable registry.

The ICMJE defines a clinical trial as any research project that prospectively assigns human subjects to intervention or comparison groups to study the cause-and-effect relationship between a medical intervention and a health outcome. Studies designed for other purposes, such as to study pharmacokinetics or major toxicity (e.g., phase I trials), would be exempt from registering trials in a public registry such as ClinicalTrials.gov.

